#### Part 2 (Efficacy)

In the Carvedilol Pediatric HF study (Shaddy 2007) for the subgroup of systemic left ventricle patients, the improvement rate of the placebo group was 51%, while the improvement rate in the carvedilol group was 64%. This was a 13% increase in absolute improvement rate over 8 month treatment period. Most of the patients in the carvedilol and placebo groups received ACEI treatment.

Table 9-1 presents the assumed underlying probabilities for each category of the primary endpoint in Part 2 (Efficacy) using data from the Carvedilol Pediatric HF study data (Shaddy 2007). It is assumed that the probability for patients receiving LCZ696 and enalapril who will have an event of death, circulatory and/or respiratory mechanical support or UNOS 1A heart transplant listing (Category 1) is similar to what was observed for the carvedilol and placebo groups in the Carvedilol Pediatric HF study. It is also assumed that the probability of patients experiencing Worsening HF (Category 2) is similar to Hospitalization for HF observed in the Carvedilol Pediatric HF study. Thus, for Categories 1 and 2, the events percentages are based on the Carvedilol Pediatric HF study (Shaddy 2007). The probability of an improved outcome for enalapril patients is assumed to be the same as for the placebo group in the carvedilol study, and the probability for the LCZ696 patients is assumed to be the same as observed for carvedilol patients in the Carvedilol Pediatric HF study. The probabilities for the worsened and unchanged categories are formed by splitting the remaining probability approximately equally for these two categories.

Table 9-1 Assumed percentage of patients in each category of the primary efficacy endpoint in Part 2 by treatment group at Month 8 (Week 32)

Category	LCZ696 (%)	Enalapril (%)
1. Clinical event – death / heart transplant listing / mech. support	6	9
2. Clinical event – WHF	10	13

Worsened functional class: NYHA/ Ross Classification or worsened PGIS

	9	14
4. Unchanged functional class: NYHA/ Ross Classification and unchanged PGIS	11	13

Improved functional class: NYHA/ Ross Classification or Improved PGIS

	64	51

The projected event percentages presented in Table 9-1 are based on the 8 month treatment period estimates. For a 52 weeks treatment period (Table 9-2), for Categories 1 and 2, the anticipated events percentages are calculated based on an exponential distribution assumption, extending from Month 8 to Month 12; and the remaining percentages within each treatment group are shared by Categories 3, 4, 5 according to their corresponding proportions at Month 8 (i.e. according to Table 9-1, 9:11:64 for the LCZ696 group, and 14:13:51 for the enalapril group). The treatment difference represented in Table 9-2 represents a Mann-Whitney-Wilcoxon Odds of 0.753.

Category	LCZ696 (%)	Enalapril (%)
Clinical event – death / heart transplant listing / mech. support	9	13
2. Clinical event – WHF	15	19

Worsened functional class: NYHA/ Ross Classification or worsened PGIS

	8.1	12.2

 
Unchanged functional class: NYHA/ Ross Classification and unchanged PGIS
 
	10.0	11.3

Improved functional class: NYHA/ Ross Classification or Improved PGIS

	57.9	44.5

The primary efficacy analysis will be a stratified Wilcoxon rank-sum test with alpha level of 0.05%, (two-sided). For the analysis of an ordered categorical endpoint with an underlying distribution as presented in Table 9-2, there is approximately 70% power with a sample size of 177 patients per group (354 total patients). Sample size calculations for the ordered categorical test (ordered categorical Mann-Whitney/Wilcoxon rank sum test) were determined using nQuery. Using a global ranked endpoint, the power under the same assumptions is expected to increase. While the exact increase in power is dependent on the distribution of the ranking within each category, simulation studies have demonstrated that the power for the global rank endpoint increases 10-20% more than with the ordered categorical analysis when the power of the ordered categorical endpoint is more than 50% (Sun 2012). Based on the assumptions stated, the power is estimated to be at least 80% for this study.

The sample size is further increased to account for a single planned interim analysis to be performed when approximately 50% of the patients (and at least 36 patients from each age group) have completed the study (50% information fraction). This interim analysis will be done to allow for early stopping of the study in the event that overwhelming positive efficacy is observed at the time of the interim analysis. Using the Lan-DeMets alpha spending function of the O'Brien-Fleming stopping boundary, a sample size of 180 patients per group (360 patients total) will provide at least 80% power for a test of the primary endpoint including a planned interim analysis. Further simulations will be performed to ensure that the estimated sample size maintains the targeted power when accounting for the interim analysis.

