#### Amendment rationale

The main reasons for this amendment are as follows:

- Based on review of Part 1 Age Group 3 PK/PD/Safety data, this amendment defines the target dose and dose regimen for Part 2 Age Group 3 to enable enrollment into Part 2 for Age Group 3. The planned target dose of LCZ696 2.3 mg/kg bid for Part 2 Age Group 3 together with the implementation of additional hypotension safety monitoring for Part 2 Age Group 3 during the initial up-titration phase is supported by the DMC and has been added to the protocol with this amendment. The DMC also supports the protocol changes with this amendment that enables Age Group 3 patients who turn 1 year old during Part 2 of the study and who are safely tolerating the LCZ696/placebo 2.3 mg/kg bid dose, to be able to up-titrate to LCZ696/placebo 3.1 mg/kg bid dose (the target dose for Age Group 2), if it is in the patient's best interest as assessed by the Investigator.
- Based upon agreement with the EMA/PDCO (PIP M04) to align the age groups with the ICH E11 guidelines on pediatric subsets, modified age groups that will be included in the analysis.
- The enrollment target of 25% ACEI/ARB naïve patients has been removed, as it is considered not attainable given that patients in this study population are often initially treated with some form of RAS inhibition when first diagnosed. Ninety percent (90%) of the patients have been randomized thus far and only a small percentage (approximately 5%) of these patients are ACEI/ARB naïve.
- The requirement to include 20% randomized patients per age group in the analysis of Part 2 has been removed. Given the challenges of recruiting patients 1 month to <1 year old (Age Group 3), it is considered not feasible to enroll 72 patients (20% of 360 patients) in this age group. The requirement for 80 patients with an event in Category 1 or 2 has also been removed. The study is sufficiently powered based on the Global Rank Endpoint and the number of patients expected to have a Category 1 or 2 event.
- Patients in Age Group 2 will be required to be Ross class II or higher at randomization. This is based on the lower event rate observed in Age Group 2 patients vs. Age Group 1 patients.
- Measurement of height has been clarified with a statement recommending use of a stadiometer for standing height measurements.

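### The power of at least 80% in protocol section 9.7 is not the power for Table 9-2; it needs a within-category effect to which 9.7 gives no value

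*Protocol*

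**What the plan says.** Protocol section 9.7, Part 2, proceeds in steps.

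- Table 9-2 gives the assumed 12-month percentages in the five categories for each arm, summarised as a Mann-Whitney-Wilcoxon odds of 0.753.
- For the five-category ordered test, "there is approximately 70% power with a sample size of 177 patients per group (354 total patients").
- It continues: "Using a global ranked endpoint, the power under the same assumptions is expected to increase".
- It then qualifies this: "While the exact increase in power is dependent on the distribution of the ranking within each category", and cites a source: "simulation studies have demonstrated that the power for the global rank endpoint increases 10-20% more than with the ordered categorical analysis", provided the ordered test has more than 50% power.
- It concludes: "Based on the assumptions stated, the power is estimated to be at least 80% for this study".
- After allowing for one interim look, it repeats that "a sample size of 180 patients per group (360 patients total) will provide at least 80% power for a test of the primary endpoint".
- It adds: "Further simulations will be performed to ensure that the estimated sample size maintains the targeted power when accounting for the interim analysis".

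No within-category distribution, effect or win probability appears anywhere in 9.7. The same section prints the two-sided alpha as 0.05%, whereas section 9.4.2 gives 0.05.

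**The concern.** Table 9-2 fixes which category patients fall into and says nothing about their order inside a category. Moving from the ordered test to the global rank breaks the ties inside categories. If treatment has no effect there, the expected difference between arms is unchanged while the variance rises, so power goes down. Power rises only if LCZ696 patients also do better within categories. The claim that power increases under unchanged assumptions, and reaches 80% on the assumptions given, therefore does not follow from the effect 9.7 quantifies.

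The figure is relied on. The rationale for Amendment 5 removed the requirement for 80 patients with a Category 1 or 2 event on the ground that "The study is sufficiently powered based on the Global Rank Endpoint and the number of patients expected to have a Category 1 or 2 event". The regional SAP (section 1.1) keeps 80% as the target of a possible blinded sample size adjustment. A neutral result would be judged against 80% power for Table 9-2, when that figure belongs to a somewhat larger effect.

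**Working it through.** **Inputs.** Table 9-2, worst to best: LCZ696 9 / 15 / 8.1 / 10.0 / 57.9%; enalapril 13 / 19 / 12.2 / 11.3 / 44.5%. Allocation 1:1 (section 5.2). Two-sided alpha 0.05 (section 9.4.2). 177 and 180 per arm (section 9.7).

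**Effect in Table 9-2.**
- P(different category, LCZ696 better) = 0.4110.
- P(same category) = 0.0117 + 0.0285 + 0.0099 + 0.0113 + 0.2577 = 0.3190. Category 5 supplies 0.2577/0.3190 = 81% of this.
- θ = 0.4110 + 0.3190/2 = 0.5705; odds (1 − θ)/θ = 0.7529. The plan's 0.753 reproduces.

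**Ordered test.** Var(θ̂) = (N+1)/(12n²) × T, with T = 1 − Σp̄³ = 0.857 (p̄ is the mean of the two arms' proportions).
- n = 177: z = 0.0705/0.02845 = 2.477; power Φ(2.477 − 1.960) = 69.8%. The plan's 70% reproduces, and simulation gives 69.9%.
- n = 180: z = 2.498; power 70.5%.

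**Global rank.** Let w be the average probability that an LCZ696 patient ranks above an enalapril patient in the same category, remaining ties counted as half. Then θ(w) = 0.4110 + 0.3190w. With each category split into K equal levels, T = 1 − Σp̄³/K²; with all ties broken, T = 1. At 180 per arm:

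| Levels per category | Power at w = 0.50 | w that matches the ordered test | w for 80% |
|---|---|---|---|
| 2 | 65.4% | 0.513 | 0.542 |
| 3 | 64.5% | 0.516 | 0.545 |
| 4 | 64.2% | 0.517 | 0.546 |
| All ties broken | 63.8% | 0.518 | 0.547 |

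Worked case, all ties broken: SE = √(361/388,800) = 0.03047. 80% needs θ = 0.5 + (1.960 + 0.842) × 0.03047 = 0.5854, so w = (0.5854 − 0.4110)/0.3190 = 0.547 and the overall odds are 0.708 (0.713 with two levels). At 177 per arm, breaking all ties with no within-category effect gives 63.1% (simulation 62.9%).

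**A plausible w.** Fitting one latent shift to Table 9-2 gives an average w of 0.536 (logistic) or 0.542 (normal). Power at 180 per arm is then 78.2-80.1% with two levels and 76.7-78.6% with all ties broken. With the 375 patients reported in the Amendment 7 rationale (187.5 per arm), 80% needs w of 0.537-0.541, and the same shifts give 78-82%.

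**Check with remaining ties and stratification.** Simulation at 180 per arm, six strata, PedsQL tie-breaking in Group 1 only, 6,000 runs per setting. Assumed, because the documents do not give them: PedsQL available in 30-60% of patients, 3-4 change levels, 4-6 baseline levels. Power was 64-65% with no effect, 72% at w of about 0.52, and 79-80% at about 0.545.

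**The cited gain.** Applied to 70%: in percentage points, 80-90%; as a relative increase, 70 × 1.10 = 77% to 70 × 1.20 = 84%. Only the first reading gives 80% at its lower end.

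**Alpha.** Taken literally, 0.05% gives Φ(2.477 − 3.481) = about 16% at 177 per arm. Only 0.05 reproduces the plan's 70%.

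**The case against.** The best defence is that 9.7 tells the reader what it is doing. It gives 70% for the ordered test, says the increment depends on the within-category ranking, and cites a 10-20% gain; 70 plus 10 is 80, so the stated assumptions can be read to include that gain. Both calculated figures are correct. The no-effect case is extreme, since a drug that moves patients across all five categories probably helps within them too. Under a smooth shift the shortfall is 0-3 points, and at 375 patients the range straddles 80%. Only a regional SAP that defers to a global one was supplied, and simulating power with an interim look would itself require a within-category distribution, so the missing simulation may exist.

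Much of this stands. The dependence is disclosed, the required effect is modest, and 80% is not shown to be out of reach. Amendment 5 also gave a second ground, the expected number of Category 1 or 2 events. Three things remain.

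- Section 9.7 says the size of the increase varies; it does not say that power can fall.
- The gain is borrowed rather than calculated for this algorithm. Category 4 is ranked first by baseline class and PGIS, which treatment cannot change (Table 6-3); PedsQL breaks ties only in Group 1 (section 6.4.1); and missing components are placed at the median (section 9.4.3).
- The promised simulations are described only as accounting for the interim analysis.

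**Conclusion.** The concern holds. Table 9-2 supports about 70% power for the ordered test, and about 64-65% for the global rank if treatment has no effect within categories. At 180 per arm, 80% belongs to a larger effect: an average within-category win probability of about 0.54-0.55, or overall odds of about 0.71 rather than 0.753. The realistic shortfall is small, roughly 77-80% under a smooth shift, and this does not show the trial to be underpowered. The fault is that the stated power is not the power for the stated effect, and the range below 80% is left out.

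The thresholds rest on a normal approximation, equal splits within categories, a single average win probability and no allowance for the interim look; the stratified simulation rests on assumed PedsQL shares and level counts. The conclusion is limited to 9.7, because the main SAP was not available. The alpha of 0.05% is a separate misprint, settled by 9.4.2.

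**What to change.** In section 9.7:

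1. Remove the statement that global-rank power increases under the same assumptions.
2. In both places where at least 80% is claimed, make it conditional on a stated within-category effect.
3. Support it with a simulation of the actual ranking algorithm (remaining ties, PedsQL in Group 1 only, median placement for missing components, stratified test). Report power over a range that starts at no within-category effect. If the main SAP already has this, refer to it.
4. Say whether the cited 10-20% is relative or in percentage points.
5. Correct the alpha from 0.05% to 0.05 two-sided, as in 9.4.2.

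The thresholds above are approximate checks, not proposed plan text. The cost is a few sentences and one short simulation; sample size, test, intended alpha and endpoint do not change.

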#### 10 Ethical considerations

#### 10.1 Regulatory and ethical compliance

This clinical study was designed and shall be implemented, executed and reported in accordance with the ICH Harmonized Tripartite Guidelines for Good Clinical Practice, with applicable local regulations (including European Directive 2001/20/EC, US CFR 21, and Japanese Ministry of Health, Labor, and Welfare), and with the ethical principles laid down in the Declaration of Helsinki.

#### 10.2 Informed consent procedures

Eligible patients/subjects may only be included in the study after providing written (witnessed, where required by law or regulation), IRB/IEC-approved informed consent, or, if incapable of doing so, after such consent has been provided by a legally acceptable representative(s) of the patient. In cases where the patient's representative gives consent, the patient must be informed about the study to the extent possible given his/her understanding. If the patient is capable of doing so, he/she must indicate assent by personally signing and dating the written informed consent document or a separate assent form. Informed consent must be obtained before conducting any study-specific procedures (e.g. all of the procedures described in the protocol). The process of obtaining informed consent and child assent where applicable must be documented in the patient source documents.

Novartis will provide to Investigators in a separate document a proposed informed consent form and age appropriate assent forms that comply with the ICH GCP guideline and regulatory requirements and is considered appropriate for this study. Any changes to the proposed consent form suggested by the Investigator must be agreed to by Novartis before submission to the IRB/IEC, and a copy of the approved version must be provided to the Novartis monitor after IRB/IEC approval.

Women of child bearing potential must be informed that taking the study treatment may involve unknown risks to the fetus if pregnancy were to occur during the study and agree that in order to participate in the study they must adhere to the contraception requirement for the duration of the study and for 7 days after study drug discontinuation. If there is any question that the patient will not reliably comply, they must not be entered in the study.

#### 10.3 Responsibilities of the Investigator and IRB/IEC

Before initiating a trial, the Investigator/institution must obtain approval/favorable opinion from the Institutional Review Board/Independent Ethics Committee (IRB/IEC) for the trial protocol, written informed consent form, consent form updates, subject recruitment procedures (e.g. advertisements) and any other written information to be provided to patients/subjects. Prior to study start, the Investigator is required to sign a protocol signature page confirming his/her agreement to conduct the study in accordance with these documents and all of the instructions and procedures found in this protocol and to give access to all relevant data and records to Novartis monitors, auditors, Novartis Quality Assurance representatives, designated agents of Novartis, IRBs/IECs, and regulatory authorities as required. If an inspection of the clinical site is requested by a regulatory authority, the Investigator must inform Novartis immediately that this request has been made.

#### 10.4 Publication of study protocol and results

The key design elements of this protocol will be posted in a publicly accessible database such as clinicaltrials.gov. In addition, upon study completion and finalization of the study report the results of this trial will be either submitted for publication and/or posted in a publicly accessible database of clinical trial results.

#### 11 Protocol adherence

This protocol defines the study objectives, the study procedures and the data to be collected on study participants. Additional assessments required to ensure safety of patients/subjects should be administered as deemed necessary on a case by case basis. Under no circumstances is an Investigator allowed to collect additional data or conduct any additional procedures for any research related purpose involving any investigational drugs under the protocol.

Investigators ascertain they will apply due diligence to avoid protocol deviations. If an Investigator feels a protocol deviation would improve the conduct of the study this must be considered a protocol amendment, and unless such an amendment is agreed upon by Novartis and approved by the IRB/IEC and health authorities, where required, it cannot be implemented.

#### 11.1 Protocol amendments

Any change or addition to the protocol can only be made in a written protocol amendment that must be approved by Novartis, health authorities where required, and the IRB/IEC prior to implementation. Only amendments that are intended to eliminate an apparent immediate hazard to patients/subjects may be implemented immediately provided the health authorities are subsequently notified by protocol amendment and the reviewing IRB/IEC is notified. Notwithstanding the need for approval of formal protocol amendments, the Investigator is expected to take any immediate action required for the safety of any patient included in this study, even if this action represents a deviation from the protocol. In such cases, the reporting requirements identified in Section 7 Safety Monitoring must be followed.

## 13 Appendix 1: Clinically notable laboratory values and vital signs

Table 13-1 Clinically notable laboratory values

Parameter	Conventional	Conventional	SI Alert	SI
	Alert Value	Units	Value	Units
Hematology				
Red Blood Cell Count	>50% increase, >30% decrease	x10E6/uL	>50% increase, >30% decrease	x10E12/L
Hemoglobin	>50% increase, >30% decrease, or any value <7	g/dL	>50% increase, >30% decrease, or any value <70	g/L
Hematocrit	>50% increase, >30% decrease	%	>50% increase, >30% decrease	L/L
White Blood Cell Count	>50% increase, >50% decrease	x10E3/uL	>50% increase, >50% decrease	x10E9/L
Platelet Count	>75% increase, >50% decrease	x10E3/uL	>75% increase, >50% decrease	x10E9/L
Chemistry				
BUN	>50% increase	mg/dL	>50% increase	mmol/L

Parameter	Conventional	Conventional	SI Alert	SI
	Alert Value	Units	Value	Units
Creatinine	>50% increase	mg/dL	>50% increase	umol/L
Albumin	<2	g/dL	<20	g/L
Glucose	>50% increase, >50% decrease, or any value <60	mg/dL	>50% increase, >50% decrease, or any value <3.3	mmol/L
Total Bilirubin	>100% increase	mg/dL	>100% increase	umol/L
AST (SGOT)	>150% increase	U/L	>150% increase	U/L
ALT (SGPT)	>150% increase	U/L	>150% increase	U/L
Sodium	>5% increase, or any value >150	mEq/L	>5% increase, or any value >150	mmol/L
Potassium	>20% increase, >20% decrease, or any value >5.3	mEq/L	>20% increase, >20% decrease, or any value >5.3	mmol/L
Chloride	>10% increase, >10% decrease	mEq/L	>10% increase, >10% decrease	mmol/L
Calcium	>10% increase, >10% decrease	mg/dL	>10% increase, >10% decrease	mmol/L
Uric Acid	>50% increase	mg/dL	>50% increase	mmol/L

Table 13-2 Criteria for clinically notable vital signs

		-	•	
Age	HR [min  ]	SBP [mmHg]	DBP [mmHg]	RR [min  ]
1-<3 months	<90, >160	<60, >95	<40, >50	<25, >60
3-<6 months	<80, >130	<60, >100	<40, >60	<20, >50
6-<12 months	<70, >130	<60, >110	<45, >70	<15, >45
1-<3 years	<60, >120	<76, >115	<45, >75	<14, >35
3-<6 years	<55, >120	<82, >120	<50, >80	<12, >30
6-<12 years	<50, >105	<90, >130	<50, >80	<10, >27
≥12 vears	<45. >95	<90. >145	<55. >90	<8. >23

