## 3.8 Risks and benefits

The study will assess the efficacy of LCZ696 in pediatric HF patients. To date no trial has demonstrated an outcome benefit of any pharmacotherapy in children with HF. Little progress has been made in improving the significant mortality and morbidity associated with symptomatic heart failure. In the 1980s, 1-year mortality rates in pediatric HF rates were 20%

to 30%, reaching 40% by 5 years. The advent of pediatric heart transplantation has decreased mortality in the first year after presentation but only where available (Hsu and Pearson 2009b).

The mortality and morbidity benefit of LCZ696 compared to the standard of care enalapril for the treatment of adult HF with reduced systolic function (HFrEF) is evident from the PARADIGM-HF study. Clinical trial data in adults demonstrate that LCZ696 has an overall safety profile generally comparable to other RAS inhibiting agents. Hypotension, hyperkalemia, renal impairment and angioedema have been identified as possible safety risks in LCZ696 studies. While the incidence rate of hypotension in study CLCZ696B2314 was higher for LCZ696 compared with enalapril, hypotension assessed as severe or serious was not higher in the LCZ696 group compared to the enalapril group. Also, no major difference was observed for hypotension leading to study drug discontinuation. In contrast, the incidence of hyperkalemia, renal impairment and cough was numerically lower in the LCZ696 group compared to the enalapril group in study CLCZ696B2314.

In the PANORAMA-HF study, two patients in the high dose group (1.6 mg/kg) of Part 1 Age Group 3 experienced AEs of hypotension. While the risk for hypotension may be lower for this age group in Part 2 of the study where study drug will be up-titrated in a step-wise manner compared to the single, high-dose setting in Part 1, additional safety measures have been implemented in an effort to decrease the risk of, and to monitor for, hypotension in Part 2 Age Group 3 patients: (1) lower target dose compared to Age Groups 1 and 2 despite similar observed exposures adjusted for dose in Part 1; (2) smaller up-titration steps compared to Age Groups 1 and 2; (3) a 4 hour observation period following the initial dose at each dose level to monitor vital signs; and (4) an additional phone call at 3 days (+/- 1 day) after each initial dose level up-titration step in order to check for symptoms of hypotension.

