#### 6.5.2 Vital signs

Vital signs include BP and pulse measurements and are assessed when a complete or abbreviated physical examination is performed. BP will be measured in the sitting position after 5 minutes of rest using an automated validated device (e.g. OMRON) or a standard sphygmomanometer with an appropriate size cuff on the non-dominant arm. Supine BP instead of sitting BP will be measured in patients who are infants or who cannot sit comfortably. Guidelines for the management of hypotension are provided in Appendix 4.

Vital signs (blood pressure and heart rate/pulse) will be collected at Visit 101, 201 during PK assessment (and unscheduled PK/PD visit if it occurs) at: 0, 30 min, 1 hr, 2 hrs, 3 hrs, 4 hrs, 5 hrs, 6 hrs, 7 hrs, 8 hrs, 9 hrs, 10 hrs, 11 hrs, 12 hrs, 18 hrs, and 24 hours post-dose LCZ696. Vital signs at 11 hrs, 12 hrs and 18 hrs are optional unless the patient physically stays on-site. The 24-hr post dose vital signs will be measured if the patient either stays on-site or returns to the site the next day. The vital signs will be collected in Part 1 and Part 2 of the study as depicted in the assessment schedule (Table 6-1 and Table 6-2).

For Part 2 Age Group 3 patients, starting with the first dose of study medication, vital signs need to be checked for up to 4 hours after the initial study medication dose at each dose level. Patients are to remain in the study site clinic for this 4-hour post-dose Vital Sign monitoring period. Vital signs are to be measured pre-dose (time 0), and post-dose at 0.5, 1, 2, 3 and 4 hours for the initial study medication dose at each dose level.

Clinically notable vital signs for this patient population are defined in Appendix 1.

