## 16 Appendix 4: American heart association (AHA) pediatric advanced life support (PALS) guidelines

Table 16-1 5th percentile systolic blood pressure table

Age	SBP percentile	SBP (mmHg)	
1 month to < 1 year	5 th	70	
1 year	5 th	72	
2 years	5 th	74	
3 years	5 th	76	
4 years	5 th	78	
5 years	5 th	80	
6 years	5 th	82	
7 years	5 th	84	
8 years	5 th	86	
9 years	5 th	88	
10 years	5 th	90	
11 years	5 th	90	
12 years	5 th	90	
13 years	5 th	90	
14 years	5 th	90	
15 years	5 th	90	

16 years	5 th	90
17 years	5 th	90

\* AHA PALS guidelines 2010 (Kleinman 2010) are widely used criteria for hypotension in acute HF patients. The formula (for 1 year and older: 70 mmHg + 2 x Age, up to age 10) is understood to provide the 5th BP percentile up to 10 years. For children 1 month to < 1 year and >10 years, the AHA PALS guidelines 2010 5th percentile is set at 70 mmHg and 90 mmHg respectively. NOTE: This formula approximates the population-based 5th percentile BP data; however, the margin of error increases with increasing age, with the PALS formula value generally providing a lower value.

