Programming note: Refer to Table 14.3-3.1.2 in CLCZ696B2319 RAP Section 14

Table 14.3-3.2.2_CHN Part 2 vital signs - clinically notable events during the double-blind epoch (Part 2 Safety Set: China Mainland Population)

Programming note: Refer to Table 14.3-3.2.2 in CLCZ696B2319 RAP Section 14

Table 14.3-3.3.2_CHN Part 2 vital signs - newly occurring clinically notable events during the double-blind epoch (Part 2 Safety Set: China Mainland Population)

Programming note: Refer to Table 14.3-3.3.2 in CLCZ696B2319 RAP Section 14

Figure 14.3-3.1.3_CHN Part 2 vital signs – heart rate – mean line plot (Part 2 Safety Set: China Mainland Population)

Programming note: Refer to Figure 14.3-3.1.3 in CLCZ696B2319 RAP Section 14

Figure 14.3-3.2.3_CHN Part 2 vital signs – systolic blood pressure – mean line plot (Part 2 Safety Set: China Mainland Population)

Programming note: Refer to Figure 14.3-3.2.3 in CLCZ696B2319 RAP Section 14

Figure 14.3-3.3.3_CHN Part 2 vital signs – diastolic blood pressure – mean line plot (Part 2 Safety Set: China Mainland Population)

Programming note: Refer to Figure 14.3-3.3.3 in CLCZ696B2319 RAP Section 14

Table 14.3-4.1.2_CHN Part 2 electrocardiogram (ECG) – test values and change from baselines – by parameter and visit (Part 2 Safety Set: China Mainland Population)

Programming note: Refer to Table 14.3-4.1.2 in CLCZ696B2319 RAP Section 14

Table 14.3-4.2.2_CHN Part 2 electrocardiogram (ECG) – new onset clinically significant abnormality (Part 2 Safety Set: China Mainland Population)

Programming note: Refer to Table 14.3-4.1.2 in CLCZ696B2319 RAP Section 14

Section 14.3.1_CHN Displays of adverse eventsTable (China Mainland Population)

Programming note: Refer to Section 14.3.1 in CLCZ696B2319 RAP Section 14

Table 14.3.1-1.2_CHN Part 2 treatment emergent adverse events – overall summary (Part 2 Safety Set: China Mainland Population)

Programming note: Refer to Table 14.3.1-1.1.2 in CLCZ696B2319 RAP Section 14

Table 14.3.1-2.2_CHN Part 2 treatment emergent adverse events (TEAEs) during the double-blind epoch (regardless of study treatment relationship) – by primary system organ class, preferred term (Part 2 Safety Set: China Mainland Population)

Programming note: Refer to Table 14.3.1-2.2 in CLCZ696B2319 RAP Section 14

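### Below 1 year of age, the clinically notable systolic limit (<60 mmHg) lies 10 mmHg under the 5th percentile (70 mmHg) that governs entry and up-titration, without explanation, so infant readings of 60-69 mmHg are not tabulated as notable

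*Protocol*

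**What the plan says.** Two protocol appendices each give a low systolic limit by age.

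**Appendix 1, Table 13-2.** Section 6.5.2 states: "Clinically notable vital signs for this patient population are defined in Appendix 1". In each row the first pair is heart rate and the second is systolic pressure. The infant rows are "1-<3 months <90, >160 <60, >95", "3-<6 months <80, >130 <60, >100" and "6-<12 months <70, >130 <60, >110". The next row is "1-<3 years <60, >120 <76, >115". The low systolic limit is then <82 mmHg for 3 to under 6 years and <90 mmHg from 6 years.

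**Appendix 4, Table 16-1.** The 5th percentile is 70 mmHg from 1 month to under 1 year, 70 + 2 x age from 1 year, and 90 mmHg from age 10. For the youngest and oldest children the footnote says "the AHA PALS guidelines 2010 5th percentile is set at 70 mmHg and 90 mmHg respectively". Exclusion criterion 8 (Section 4.2) excludes pressures below this value. Table 3-3 (Section 3.1) requires systolic pressure above it for initiation and up-titration.

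**Why infants matter here.** Section 3.8 reports that "two patients in the high dose group (1.6 mg/kg) of Part 1 Age Group 3 experienced AEs of hypotension" and lists added safety measures for that age group in Part 2. Appendix 13 requires blood pressure before dosing and at 0.5, 1, 2, 3 and 4 hours after the first dose at each dose level, recorded on the CRF.

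**Reporting.** The supplied SAP is a regional supplement. Its Section 3 lists "Part 2 vital signs - clinically notable events during the double-blind epoch" and a companion table of newly occurring notable events, both by reference to a main RAP that was not supplied.

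**The concern.** The protocol works with one low-pressure limit for deciding who may enter and who may go up a dose level, and another for deciding which readings are counted as notable. From age 1 upward the second is at least as sensitive as the first, so every value below the 5th percentile is also notable. Under 1 year the order is reversed, and no passage says this was intended.

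A reading of 60-69 mmHg can therefore stop an infant's up-titration and yet not be counted in the notable-value table. This falls on the age group for which the protocol added post-dose blood pressure checks because of hypotension. A reader of that table would see infant counts based on a limit stricter than the 5th percentile beside older-child counts based on a limit looser than, or equal to, it. At stake is the clarity of the descriptive safety record in infants. The primary endpoint is not touched.

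**Working it through.** **1. Reproduce Table 16-1.** Inputs: 70 mmHg below 1 year; min(70 + 2 x age, 90) from 1 year. This gives 70; then 72, 74, 76, 78, 80, 82, 84, 86, 88 for ages 1 to 9; then 90 for ages 10 to 17. All 18 rows match the table.

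**2. Subtract.** Difference = Table 13-2 low systolic limit minus Table 16-1 5th percentile (mmHg).

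| Age | Table 13-2 | Table 16-1 | Difference |
|---|---|---|---|
| 1 month to <1 year (three rows) | 60 | 70 | -10 |
| 1 year | 76 | 72 | +4 |
| 2 years | 76 | 74 | +2 |
| 3 years | 82 | 76 | +6 |
| 4 years | 82 | 78 | +4 |
| 5 years | 82 | 80 | +2 |
| 6 years | 90 | 82 | +8 |
| 7 years | 90 | 84 | +6 |
| 8 years | 90 | 86 | +4 |
| 9 years | 90 | 88 | +2 |
| 10 to 17 years | 90 | 90 | 0 |

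The sign is negative only in infants.

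**3. Which whole-mmHg readings are below the 5th percentile but not notable?** Infants: 60 to 69, ten values. Ages 1 to 17: none.

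**4. Boundary values.** Table 3-3 requires a value strictly above the 5th percentile. An infant reading of exactly 70, or a reading of exactly 90 from age 10, therefore also fails up-titration without being notable. These single values do not fail exclusion 8, which applies only below the 5th percentile. The ten-value band that fails both criteria exists only under 1 year.

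**5. Where such readings can arise.** Appendix 13 gives five post-dose readings at each of up to four initial dose levels (1x to 4x), so at most 5 x 4 = 20 post-dose readings per infant. This is a ceiling, since a start at 2x is allowed.

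**6. Crossing the first birthday.** Every Age Group 3 child followed for 52 weeks turns 1 on study. At that point the Table 13-2 limit moves by 76 - 60 = 16 mmHg, while the Table 16-1 value moves by 72 - 70 = 2 mmHg. If age at the reading is used, a pressure of 60-75 mmHg goes from not notable to notable with no change in pressure. The documents do not say which age applies.

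**The case against.** **Different purposes can have different limits.** One table governs entry and titration, the other flags values for reporting, and no passage says they must agree. They also differ at ages 1 to 9, and potassium too has different cut-offs for different uses (exclusion and notable >5.3 mmol/L, up-titration at or below 5.4). This stands: the finding is an unexplained inconsistency, not a breach of a stated rule. It does not explain why the direction reverses only under 1 year.

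**Low pressure in infants is reported elsewhere.** A reader might infer that the safety report misses infant hypotension. The documents do not support that. Readings below 60 mmHg are still notable. Hypotension is an adverse event of interest (Section 9.5.2), and the SAP lists a table of hypotension-related events and systolic values by visit. The DMC reviews safety data regularly. Two limits on this reply remain. Visit summaries do not count patients below a limit. Section 7.1 also lists the clinically notable ranges among the things used to identify clinically significant test results, so adverse event reporting is not wholly independent of Appendix 1.

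**The main SAP and RAP are not supplied.** This stands. The regional table titles name no age split, and it cannot be confirmed that the main notable-value table is split by age group, includes the 4-hour readings, or applies Table 13-2 unchanged. The last is inferred from Section 6.5.2. The hypotension table may already use a systolic criterion.

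**No bias between arms, and few infants.** Both arms share the same limits, and Section 9.5.2 plans no formal inference for safety. Amendment 5 opened Part 2 to Age Group 3 when about 325 patients were enrolled; 375 randomized patients received drug. Roughly 375 - 325 = 50 patients of all ages followed, so the infants among them are probably few.

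**Appendix 4 is not thereby the right limit.** A reader might infer that Table 13-2 is simply wrong. The Table 16-1 footnote itself calls its formula an approximation. The documents do not settle which value should hold.

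**Conclusion.** The point holds in a limited form. For children under 1 year the notable systolic limit is 10 mmHg below the 5th percentile used for exclusion 8 and Table 3-3. At ages 1 to 9 it is 2 to 8 mmHg above, and from age 10 it is equal. The documents give no reason. Followed as written, infant readings of 60-69 mmHg fail the protocol's own entry and up-titration limit but are not tabulated as clinically notable.

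The arithmetic is exact. The effect on the tables rests on the assumption that the main RAP applies Table 13-2 as printed. The number of infants or readings affected cannot be worked out from the documents. The consequence is a gap in one descriptive safety output for the age group under closest watch for hypotension; infant low pressure is not lost from the safety report as a whole, and the comparison between arms is not biased. It is worth correcting because the correction is cheap.

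**What to change.** 1. Reconcile Table 13-2 with Table 16-1, and with Table 3-3 and exclusion 8 which use it, for children under 1 year, or state why they differ. This review does not say which limit should hold.
2. Whatever limits are kept, add to the Part 2 vital sign output the number of patients with any post-baseline systolic value below their Appendix 4 value, by arm and age group, including the Age Group 3 4-hour post-dose readings. State whether the limit follows age at randomization or age at the reading.
3. If the main RAP already contains such a count, a cross-reference is enough.

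Cost: one clarification and one extra descriptive table from data already on the CRF; closed recruitment is no obstacle. The downside is that more infants will be counted as having low readings.
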